**Risk vs. Potential Benefit.** The proposed research poses "minimal risk" to subjects. There are no experimental procedures involved in this study. The potential risks to study participants include loss of privacy and confidentiality. There are no economic and minimal social risks of participating in the study. The surveys will not ask very sensitive questions and subjects can refuse to answer any question(s). The potential risks associated with the individual interviews include psychosocial stress (any research project with direct contact with human subjects contains some risk of deleterious effects due to psychosocial stress). This is true for both usual care as well as intervention groups.

Mindfulness-based interventions are regarded as relatively safe interventions. A 2018 systematic review examining the safety of randomized controlled trials of mindfulness-based interventions found very few adverse events, with no significant differences in reported adverse events between intervention and control groups. Nonetheless, we have developed a crisis management protocol to address issues involving participant safety and systematically collect safety information, including severe adverse events (SAEs), unanticipated problems (UAPs), and adverse events (AEs). In the follow up questionnaires, participants will be asked to report side effects/adverse events related to the interventions by choosing from a list generated from the literature and the investigators' experience (see below).

Since you started your participation in the study have you experienced any of the following. Check all that apply.

- 1. Increase in disturbing memories
- 2. Feeling more upset than usual when something reminded you of the past
- 3. Increased feelings of sadness
- 4. Increased feelings of anxiousness

5. Seizures

- 6. Feeling more tired or fatigued than usual
- 7. Feeling more isolated or lonely

8. Other physical or mental symptoms; please specify: \_\_\_\_\_\_

If yes, please explain further:

Specifying conditions that would trigger an immediate suspension of the research is not applicable to this minimal risk study. If information does arise that necessitates communication, the study team will contact participants by phone and providers via encrypted email.

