Study staff will conduct a medical chart review in the electronic medical record of all participants who meet the screening criteria, in order to exclude any patients with active psychotic symptoms, suicidality, severe depression, and/or active manic episode or poorly controlled bipolar disorder. Some experts consider these disorders as contraindications for MBIs.

We will not exclude Veterans who are prescribed medication or receiving other treatments for chronic pain. However, we will collect information about medication and other treatment use and take this into account in our analyses.

Besides meeting all eligibility criteria, PCT participants must also complete the baseline survey before randomization will occur.

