For intervention participants, all mobile app data collected will occur via a secure cloud-based application designed by MEI Research Ltd to support data capture for research studies and will be accessed as part of the mobile application. Because we are collecting mobile app data, we will be temporarily storing IP addresses, URLs, device identifiers, serial numbers, since this type of mobile app data may need to be collected as participants use their smartphones to interact online with the study application. The secure cloud-based application designed by MEI Research Ltd. to support data capture for this research study must be accessed as part of the study intervention. As the participant's smart phone engages online with the study application some information (IP addresses, URLs, device identifiers, serial numbers) may be captured by the cloud-based application in order appropriately deliver the correct content to the participant's device. However, we will not use this information in our research or transfer it to the VA. Co-I [name] has successfully conducted VA-funded studies using this data collection approach.

**Data coordination and management.** Data collection and management will be overseen at the Minneapolis VA HSR&D Center of Innovation (COIN) by [name]. Regular meetings of investigators and study staff within and between sites will take place to routinely review data collection and management issues. To prevent improper use of any data collected for research projects conducted at the Minneapolis COIN we will use a combination of local Minneapolis VA secure servers as well as the national secure VA Informatics and Computing Infrastructure (VINCI) and the secure Qualtrics FedRAMP system in the VA cloud. The local VA secure servers facilitate data collection and provide a platform for the customized research tracking application, while the VINCI platform provides a robust environment for pooling the primary research collected data with direct connections to daily or weekly updated mirrors of nearly the entire VHA EHR. VINCI also provides access to extensive storage area networks, drives, file shares, databases, SharePoint for collaboration and correspondence sites, SAS/Grid, and servers containing virtual machines with an extensive collection of software called the VINCI Workspace. We will request access to the Joint Legacy Viewer (JLV) in order to capture the

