We will use electronic medical data from VA health care records to assess other measures of chronic pain burden including change in analgesic use (including opioids), and frequency and health care utilization (e.g. MRIs, injections, hospitalizations, surgery). Among those prescribed opioids, we will assess change in opioid use from baseline using VA pharmacy dispensing data. Opioid daily dose at any given time will be calculated as the mean dose over the prior 90 days. Established conversion tables will be used to calculate morphine-equivalent (ME) mg. Receipt

LAMP Version 16, March 25, 2024 VA Central IRB Protocol Template – version 10/26/2012 Page 42 of 60

of pain-related services outside of intervention visits will be estimated by capturing pain-related specialty visits and pain-related mental health visits. Complementary therapies are not all well captured in VA databases, but therapies with specific codes (e.g., acupuncture) will be assessed. Other complementary services may be variably recorded under general codes; for example, yoga could be coded as a recreational therapy visit.

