## 5.7 Withdrawal of Subjects

Participants can withdraw or be terminated from the study at any point. They can withdraw from the study at any time they feel uncomfortable or choose to do so. We anticipate terminating participation if:

- 1. The participant displays abusive behavior toward other participants and/or the study staff.
- 2. Study staff believe the participant cannot meaningfully participate in the study.
- 3. Study staff believe it is not in the participant's best interest to stay in the study.
- 4. The participant becomes ineligible to participate.
- 5. The participant does not follow instructions from the researchers.
- 6. The study is suspended or canceled.
- 7. Any other condition that renders patients unable to benefit from treatment.
- 8. The participant chooses to withdraw consent.

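### Psychosis, mania and suicidality are screened out at entry but have no named item in scheduled follow-up safety collection, and depression scores have no stated safety use

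*Combined protocol and SAP*

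**What the plan says.** **At entry.** Section 5.4a has staff review the medical record of everyone who passes the screener, to "exclude any patients with active psychotic symptoms, suicidality, severe depression, and/or active manic episode or poorly controlled bipolar disorder". The reason follows: "Some experts consider these disorders as contraindications for MBIs".

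**At follow-up, the checklist.** Under Risk vs. Potential Benefit (Aim 1) in section 5.1, the follow-up questionnaires ask for adverse events "by choosing from a list generated from the literature and the investigators' experience (see below". The list has seven named items and an eighth for other physical or mental symptoms, in free text. The named item closest to an entry exclusion is "Increased feelings of sadness".

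**At follow-up, other sources.** Table 2 gives three adverse-event sources at 10 weeks, 6 months and 12 months: survey, Veteran report, and events reported to the Central IRB. Section 5.5a invites participants to report problems to facilitators or the coordinator throughout. Section 5.1 has staff follow a protection protocol if self-harm ideation or distress appears in group or by phone.

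**At follow-up, the EHR.** Table 2 marks mental health characteristics at baseline only. The follow-up EHR measures in 5.5a cover analgesics and utilisation as pain burden, and mental health care enters by "capturing pain-related specialty visits and pain-related mental health visits". The same section describes a platform with "direct connections to daily or weekly updated mirrors of nearly the entire VHA EHR".

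**Depression** is a secondary outcome, surveyed with PROMIS-29 at baseline and all three follow-ups.

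**Termination.** Section 5.7 lists "The participant becomes ineligible to participate" among the grounds for ending participation.

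**The concern.** By its own eligibility rule, the protocol links a short list of psychiatric conditions to the intervention. A reader of the results will want to know whether those conditions appeared during the trial and how the arms compare. For psychosis, mania and suicidality, no scheduled follow-up measure asks.

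Two things are at stake. First, a report of few or no such events would be hard to interpret, because the plan gives no way to tell absence from non-ascertainment. Second, the chance of an event coming to staff attention differs by arm, so a difference in counts could arise from contact alone. Both matter here because the introduction describes Veterans in mindfulness groups as having high rates of PTSD (nearly 75% in one cited study) and depressive disorder (59%), and because the programme is meant for wide delivery in the VHA.

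**Working it through.** The plan states no figure on this point, so there is none to reproduce. The check sets the entry exclusions against each follow-up source and then asks how much incomplete capture could matter.

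**Step 1. Entry exclusions against scheduled follow-up**

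| Condition | Named checklist item | Other scheduled measure | Remaining routes |
|---|---|---|---|
| Psychosis | none | none | free-text item, spontaneous report, serious-event reporting |
| Mania | none | none | the same |
| Suicidality | none | none in Table 2 | the same, plus disclosure in group or by phone |
| Severe depression | sadness, a loose match | PROMIS-29 at 3 of 3 follow-ups | the same as psychosis |

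No named item matches an exclusion exactly, and one of the seven matches loosely. The pooled COVID-19 plan in section 5.6 lists presence of suicidal ideation as a clinical variable but gives no instrument or time point. Table 2 has no row for it and places the COVID-19 questions at baseline only.

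**Step 2. Staff contact by arm (section 5.1)**

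Mobile+Group has 8 group sessions. Mobile has 3 scheduled calls. For usual care no scheduled intervention contact is described. Disclosure to staff therefore has unequal opportunity by design.

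**Step 3. Illustration of size**

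Inputs from the documents: 250 per arm gives 2 × 250 = 500 MBI participants; 950 randomised 1:1:1 gives 950 × 2/3 = 633.

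Assumed inputs: incidence *p* = 1% for psychosis, mania and suicidality together (depression is left out because it is measured), and capture fraction *c*. Neither is in the documents.

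Expected events = *n* × *p*: 5.0 and 6.3. Chance of seeing none = (1 − *pc*)^*n*.

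| Capture *c* | Basis (assumed) | *n* = 500 | *n* = 633 |
|---|---|---|---|
| 25% | half return a survey, half of those write the event in | 0.9975^500 = 0.29 | 0.9975^633 = 0.20 |
| 44% | three surveys at 50% return, independent: (1 − 0.5³) × 0.5 = 0.4375 | 0.995625^500 = 0.11 | 0.995625^633 = 0.06 |
| 100% | full ascertainment | 0.99^500 = 0.007 | 0.99^633 = 0.002 |

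The 25% row is pessimistic. Section 5.6 plans for at most 20% missing follow-up and cites past completion above 90%. With 80-90% return and the same 50% write-in rate, *c* is 40-45% and the chance of seeing none is about 6-14%. No row credits the non-survey routes.

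Zero events under full ascertainment gives a one-sided 95% upper bound of 1 − 0.05^(1/*n*): 0.60% for 500 and 0.47% for 633. Under partial capture the bound on the true rate is this divided by *c*. At 44% that is 0.60/0.4375 = 1.4% and 0.47/0.4375 = 1.1%. The plan offers no means of estimating *c*, so the bound cannot be stated.

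**The case against.** The strongest reply is that follow-up safety collection is not empty. Depression and PTSD symptoms are measured in every arm at every follow-up, and the checklist asks about sadness. Section 5.6 also summarises outcome distributions across time points, so the depression data are not confined to a mean difference. Adverse events come from Veteran report and IRB-reported events as well as surveys. Staff are trained on a crisis procedure, 5.3a describes escalation when safety is a concern, and section 6.0 covers serious-event reporting. A crisis management protocol is mentioned but is not among the documents, and it may contain more.

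All of that stands, and it rules out two readings a reader might be tempted by. One is that none of the excluded conditions is followed systematically; for depression that is false. The other is that these events would go largely unreported; the documents do not establish it, because several reactive routes exist and their yield is unknown.

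It is also fair that 5.4a excludes active conditions because some experts regard them as contraindications. It does not say that MBIs cause new onset, and nothing here should be read that way.

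What the reply leaves unanswered is narrower. For psychosis, mania and suicidality every described route depends on the participant volunteering the event or on its reaching staff by chance, and scheduled opportunity for that differs by arm. For depression, no cut-off or safety reading of the scores is given.

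**Conclusion.** The concern holds in this limited form. Three of the four conditions excluded at entry as possible contraindications have no named item in scheduled follow-up safety collection. The fourth is measured, but no severity threshold or safety use is stated. A between-arm comparison of the first three would be incomplete and would partly reflect staff contact, which could hide events in a low-contact arm or create an apparent excess in a high-contact one.

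The size is not known. The chance of seeing no event in the MBI arms runs from about 20-29% down to under 1% as capture goes from 25% to 100%, at an assumed 1% incidence. The better-supported survey assumptions put it near 6-14%, before any credit for other routes. These figures rest on assumed incidence and write-in rates and, in the 44% row, on independent survey return. They show why capture matters and do not predict what the trial would miss.

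This is a worthwhile, inexpensive improvement to safety reporting. It does not affect the validity of the primary comparison.

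**What to change.** 1. **Common EHR query.** Add to section 5.5a and Table 2 one query, run after each participant's 12-month date and identical for all three arms, for new diagnoses in the 5.4a categories between randomisation and 12 months. Fix the code list and the look-back that defines new before extraction. Tabulate by arm with exact confidence intervals, as a descriptive safety outcome.
2. **Depression as safety data.** From the score already collected, report by arm the number who were below a prespecified severe range at baseline and reach it at any follow-up, with the number assessed.
3. **Reconcile.** Section 5.6 lists suicidal ideation for the pooled COVID-19 dataset, and Table 2 gives no source or time point for it. State both, or remove the variable.

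These are reporting changes and set no clinical rule.

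**Cost.** One query on a platform the team already plans to use, and two descriptive tables, with no added participant burden. The query depends on the study-wide HIPAA waiver that section 5.3a says is being sought.

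**Limits to state in the report.** Codes miss care outside VA, under-record suicidality, and do not reproduce the chart judgements of active or poorly controlled disease. They may also be recorded more often in arms with more staff contact, since staff can escalate to VA teams. The query makes ascertainment more even across arms but should not be described as equal.

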## 5.2 Recruitment Methods and Participant Enrollment

#### Aim 1

We anticipate recruiting up to 950 participants from our 4 sites, using our proactive recruitment protocol (see below). The subject population for our study will be chronic pain patients from the Minneapolis, Durham, Indianapolis, and Los Angeles VA medical centers They will be 18 years or older. Using this protocol, we plan to recruit up to 950 participants with about 40% being female. Participants will be randomized to one of the 3 study arms and asked to participate in the subsequent intervention. Thus 250 participants will be in each arm (Mobile+Group, Mobile, and UC). All participants will be asked to complete the screener, and then complete the baseline and 10-week, 6-month, and 12-month follow-up surveys. Participants will be given \$25 for each survey they complete (possible total of \$100). Completion of the eligibility components will result in randomization to one of the three study arms, (Mobile+Group MBI, Mobile MBI, or UC (1:1:1)).

#### Proactive recruitment protocol.

For the PCT, these patient study IDs will be imported into Qualtrics FedRAMP. Participants will be recruited using two different approaches. All participants will receive pre-notification of the study by postal mail. In Approach #1 ("postal mail-only"), introductory letters will be mailed that include instructions for accessing the study website via a secure URL, an opt-out option, and information about the monetary incentive that study participants will receive. Participants will also be sent an information sheet, informational newsletter, and general introductory brochure. In Approach #2 ("postal mail + email), participants will be notified about the study by postcard, which will: 1) inform them that they will be receiving an email inviting them to be in a research study for Veterans and 2) provide instructions for opting out via email or phone. This postal mailing will be followed by an email, using the email in the VA EHR, which will contain the same information (in email form) provided to those in paper form in Approach #1. This "email recruitment packet" will contain instructions for accessing the study website via a secure URL (which has been approved by the ISSO in a prior amendment) and direct links to the information sheet, informational newsletter, and general introductory brochure, which reside on the website. The email will also contain an opt-out option, information about the monetary incentive that study participants will receive, and information contained in the paper brochure. Emails will be sent using Qualtrics FedRAMP. Qualtrics FedRAMP is authorized by an ATO to collect data from Veterans and store data on VA cloud servers.

In Approach #1, participants who do not respond will be sent a reminder postcard to encourage a response of some sort. In Approach #2, participants who do not respond will be sent reminder postcards and/or emails to encourage a response of some sort. Participants who log into the study website will then be directed to the study screener. Study staff will potentially follow-up with participants who start the screener and/or baseline but do not finish, as well as participants who do not respond in any way. Communications will include answering participant questions, encouraging people to do the screener and baseline online, reviewing what is coming next in the study (medical chart review, baseline survey, follow-up call for randomization, etc.), and

asking questions about how to improve the recruitment process. Trained study staff will respond to participants who reach out via email or phone with questions.

Refer to the 5.4 Inclusion/Exclusion section below for eligibility criteria.

#### Aim 2a: Pre-implementation data will be collected from Veteran participants via survey.

Pre-implementation data will be collected from Veteran participants as an "extra" survey intervention participants can opt into at the end of their 10-week follow-up survey. The pre-implementation survey will be administered using Qualtrics FedRAMP, as are the other surveys in this study. Participants will be paid an additional \$25 for completing the pre-implementation survey. We will send them minimal text and email reminders if they indicate they would like to complete the extra survey but don't do so within a few days.

# Aim 2b: Pre-implementation data will be collected from VA employee stakeholders using rapid qualitative analysis methods

**Recruitment protocol.** We will recruit a total of n=30 employee stakeholders by email. The email will come from the Principal Investigator ([name]) and will invite the participant to completed a semi-structured interview (lasting 30-45 minutes), conducted over video, aimed at helping the research team identify barriers and facilitators to implementing a new mindfulness program for Veterans with chronic pain, within the VHA. Participants will also be asked to complete a short demographic questionnaire only using VA-approved Qualtrics FedRAMP. Limited reminder emails will be sent to non-responders.

Study Procedures and Materials. All qualitative interviews will be video and/or audio recorded using VA-approved technology (e.g., Microsoft Teams). Meeting times will be agreed upon ahead of time between facilitators and stakeholders. All reasonable efforts will be made to work with each stakeholders' schedule and preference for meeting.

# 5.3 Informed Consent Procedures 5.3a. Informed Consent Procedures for Veterans (Aims 1 and 2a)

We will seek waivers of both informed consent and HIPAA authorization for the initial search of EHRs for potential participants. The research meets all of the criteria for requesting a waiver of the informed consent process, including involving no more than minimal tangible or intangible risk to the participants, the waiver will not adversely affect the rights and welfare of the participants, the research could not practicably be carried out without the waiver, and when possible, participants will be provided with additional pertinent information after participation.

The information requested in the waivers is needed on all identified subjects so that we are able to conduct analyses to assess and correct for non-response bias. Specifically, we plan to conduct analyses to determine whether the participants who responded to our request for
participation differ from those who did not respond, on a number of characteristics that are available through the administrative data set (e.g., age, healthcare comorbidity). If we do find that non-response bias exists, we would then be able to statistically adjust for this bias using the data on non-respondents available from the administrative dataset. Requiring HIPAA authorization for the VA administrative data requested in this waiver from subjects would not allow us to conduct these analyses. In addition to the initial search of EHRs, we are seeking a waiver of HIPAA authorization for the entire study.

We are seeking a waiver of documentation of informed consent for the PCT portion of the study, the "pre-implementation" follow-up surveys with a portion of intervention participants, and recontacting a portion of the pre-implementation follow-up survey completers. We are not asking sensitive questions in this survey. Asking subjects to return signed consent and authorization documents for this minimal risk study would dramatically reduce response rates and introduce bias. Additionally, the signed consent form would potentially increase risk for loss of privacy as all identifying information will be destroyed as soon as feasibly possible. Participants will receive mailed, pre-notification (postcard or letter, depending upon the recruitment approach; see Section 5.2) that contains an opt-out option for those who do not want to be contacted any further. Participants in recruitment approach #1 (postal mail only) will receive, with their prenotification letter, an information sheet containing: 1) information explaining the risks and benefits of study participation, 2) their rights as study participants and their privacy rights and 3) required elements of informed consent. Participants in recruitment approach #2 (postal mail + email) will be given a link to an electronic copy of the information sheet, as part of their email recruitment packet. Randomized participants in recruitment approach #2 will be sent a paper copy of the information sheet in their randomization packet.

Prior to randomization, participants will be contacted via a phone call in which all participation components will again be reviewed. This will include requiring participants to provide an emergency contact person and explaining that study staff will do the following if they are concerned about a participant's or others' safety. Study staff will explain: If we are concerned for your immediate safety, we may try calling, and/or emailing you, contacting your emergency contact person, and will then escalate further (for example, asking the Veteran Crisis Line staff to contact you, asking the Suicide Prevention team at your VA site to contact you, or asking your local police to do a wellness check) as it seems necessary to protect you or others. Only if participants agree to continue, they will be randomized a study group.

